4.4.5 Safety Analyses

All adverse events and serious adverse events will be listed. Adverse events include the acupuncture-related adverse events and other adverse events.

5. The Summary of Changes of Final SAP

As compared to the original statistical analysis plan (SAP) published in the *Front. Med.* ([name], [name], [name], et al. Effects of Electroacupuncture on Opioid-Induced Constipation in Patients with Cancer: Study Protocol for a Multicenter Randomized Controlled Trial. Front Med. 2022), the present finalized SAP had made a few amendments. The major updates were provided in Table 1.

Table 1. MAJOR UPDATES OF THE ORIGINAL SAP

No.	Item	Original Version	Final Version
1	Missing	Missing data on the primary	As a sensitivity analysis, missing
	data	outcome will be imputed using	data on the primary outcome will be
		the multiple imputation method	imputed using the multiple
		under the missing at random	imputation method under the
		assumption.	missing at random assumption.
2	Primary	The primary outcome will be	The primary outcome will use a
	outcome	evaluated using the x^2 test.	generalized linear model with a
			binomial distribution and identity
			link.
3	Safety	AE incidences for each	AE data will be provided for
	outcome	treatment group will be	descriptive purposes only.
		compared using Fisher's exact	-
		test.

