In traditional Chinese medicine, acupuncture has been used to treat gastrointestinal disease, including constipation, for thousands of years. According to two systematic reviews, acupuncture can improve spontaneous bowel movements (SBMs) in functional constipation . Additionally, the results of our study indicated that electroacupuncture (EA) could increase complete spontaneous bowel movements (CSBMs) and SBMs, with a long-term effect that continues for 24 weeks after treatment ceased among patients with chronic, severe functional constipation . Through stimulation of the somatic and peripheral nervous systems, acupuncture can facilitate the gut motility and improve

gastrointestinal function . The effectiveness of acupuncture for OIC is currently lacking evidence. The purpose of this study is to compare the efficacy and safety of EA with sham acupuncture (SA) in the treatment of OIC in cancer patients.

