### 3. Safety Assessment

All adverse events (AEs) will be recorded throughout the whole trial in Adverse Event Form (AEF) by patients themselves and outcome assessors. In our trial, the serious AEs will be defined as events that cause death, exacerbation of the preexisting condition, interruption of treatment, prolongation of existing hospitalization, permanent disability or damage, or required medical intervention to prevent one of the above outcomes. AEs will

be categorized as treatment related or non-treatment related based on its potential association with acupuncture needling procedure by acupuncturists and related specialists within 24 hours. The treatment related AEs defined as follows: dizziness, fainting, localized hematoma, localized minor infection, or some discomforts after acupuncture. Safety assessments also include an 11-point NRS (0 indicates no pain, and 10 indicates the severest pain) to evaluate the intensity of cancer pain. The mean and largest intensity of cancer pain during the preceding week will be evaluated at baseline, as well as weeks 2, 4, 6, 8 and 16.

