4.4 Statistical Analyses

4.4.1 The General Principle

Summary tables (descriptive statistics and/or frequency tables) will be provided for all variables at different endpoints. For continuous variables, means and standard deviations will be presented, unless the variable has a skewed distribution, in which case medians, 25th and 75th percentiles will be presented. For categorical variables, the number and percentage of participants within each category will be presented. For each variable (continuous or categorical), the number of missing values will be reported.

Statistical Comparisons Between Groups

Continuous variables will be compared using a two-sample *t*-test or Wilcoxon rank-sum test if data show serious deviations from a normal distribution. Categorical data or ordinal data will be compared using a Wilcoxon rank-sum test, chi-square test or Fisher's exact test, as appropriate. All tests will be two-sided.

For the analysis of the primary and secondary outcomes, estimated treatment differences and associated 95% two-sided confidence intervals will be presented.

Analysis Software

For all statistical analyses, SAS 9.4 software will be used. All hypothesis testing will be carried out at the 5% (2-sided) significance level.

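### Cancer-pain NRS, a protocol safety assessment, is left to the generic rules of SAP 4.4.1: an unadjusted comparison with no promised EA-SA difference or 95% CI (minor)

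*SAP*

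**What the plan says.** Protocol section 3 puts pain under safety: "Safety assessments also include an 11-point NRS (0 indicates no pain, and 10 indicates the severest pain) to evaluate the intensity of cancer pain". Two measures are taken: "The mean and largest intensity of cancer pain during the preceding week will be evaluated at baseline", and again at weeks 2, 4, 6, 8 and 16. Protocol 2.2 gives the purpose of the study as to "compare the efficacy and safety of EA with sham acupuncture (SA) in the treatment of OIC".

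SAP 4.4.5 has two sentences, both on adverse events. The first reads "All adverse events and serious adverse events will be listed"; the second divides events into acupuncture-related and other. The pain NRS is not named there or anywhere else in the SAP.

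SAP 4.4.1 therefore governs pain by default:
- Summaries: "Summary tables (descriptive statistics and/or frequency tables) will be provided for all variables at different endpoints". Means and SDs are used "unless the variable has a skewed distribution, in which case medians, 25th and 75th percentiles will be presented".
- Comparison: a two-sample t-test, or a "Wilcoxon rank-sum test if data show serious deviations from a normal distribution". No baseline covariate is mentioned.
- Estimates and intervals: "For the analysis of the primary and secondary outcomes, estimated treatment differences and associated 95% two-sided confidence intervals will be presented".

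**The concern.** Every participant takes opioids for cancer pain, so a reader of the safety results will ask whether pain control was kept while constipation was treated. That calls for an estimate of the EA-SA difference and the range of worsening that the data exclude. A non-significant test in a trial of about 100 patients does not supply this.

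The generic route leaves three gaps:
- No difference or interval is promised for pain.
- It is not stated whether scores or changes from baseline are compared. With two measures, five post-baseline visits and two scales, that leaves 2 × 5 × 2 = 20 possible comparisons, none named as the main one.
- The baseline score is collected but not used as a covariate.

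Pain also needs to be read beside opioid dose, because worsening pain can be met by a higher dose and then leave the NRS flat. Item (13) of the other pre-specified outcomes already captures dose changes of 30% or more.

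**Working it through.** **Step 1. Does the interval rule reach pain?** The primary outcome (protocol 2.4.4.1) is bowel-movement response. Secondary outcomes (1) to (12) cover bowel movements, stool form, straining, the two PAC questionnaires, global assessment and rescue medicine. Items (13) to (16) cover opioid dose, anti-tumour therapy, belief in acupuncture and blinding. Pain is in none of these lists, so the interval rule in SAP 4.4.1 does not cover it.

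**Step 2. What can a reader recover?** If pain is roughly normal, 4.4.1 yields means, SDs and n, and an unadjusted interval can be worked out from them. If pain is skewed, 4.4.1 gives medians and quartiles, and the usual normal-theory interval cannot be worked out from those. A baseline-adjusted estimate is available in neither case.

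**Step 3. Sample size per arm.** The plan's own figure reproduces. With 14% on SA, 14 + 31.4 = 45.4% on EA, two-sided 0.05, 90% power and unpooled variance:

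n = (0.14×0.86 + 0.454×0.546) × (1.960 + 1.282)² / 0.314² = 0.3683 × 10.51 / 0.0986 = 39.3, so 40 per arm.

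Then 40/0.8 = 50 per arm, or 100 in total. Pain precision is therefore shown at 50 per arm and at 40 (after 20% loss).

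**Step 4. Assumptions.** The documents give no SD or correlation for pain. SD 2 is used, with 1.5 and 2.5 as the range. An even spread over the integers 0 to 6 has variance (7² − 1)/12 = 4, so SD 2. Exclusion (11), which removes opioid-refractory average pain of 7 to 10, makes that a rough guide for mean pain at baseline only. Correlation ρ is taken as 0.3, 0.5 and 0.7.

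**Step 5. 95% half-widths.** Unadjusted score at one visit: 1.96 × SD × √(2/n) = 1.96 × 2 × √(2/50) = 0.784. The other half-widths multiply this by:
- change score: √(2(1−ρ)) = 1.183, 1.000, 0.775
- baseline-adjusted: √(1−ρ²) = 0.954, 0.866, 0.714
- mean of k = 4 visits (weeks 2-8), unadjusted: √((1+3ρ)/4) = 0.689, 0.791, 0.880
- the same mean, baseline-adjusted: √((1+3ρ)/4 − ρ²) = 0.620, 0.612, 0.534

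The last two assume equal correlation among all visits, including baseline.

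| SD 2, 50 per arm | ρ 0.3 | ρ 0.5 | ρ 0.7 |
|---|---|---|---|
| Per visit, unadjusted score | 0.78 | 0.78 | 0.78 |
| Per visit, change score | 0.93 | 0.78 | 0.61 |
| Per visit, baseline-adjusted | 0.75 | 0.68 | 0.56 |
| Weeks 2-8 mean, unadjusted | 0.54 | 0.62 | 0.69 |
| Weeks 2-8 mean, baseline-adjusted | 0.49 | 0.48 | 0.42 |

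Per visit, adjustment is worth raising 50 per arm to 50/(1−ρ²) = 55, 67 or 98.

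Sensitivity, per visit, unadjusted against adjusted:
- SD 2, 40 per arm: 0.88 against 0.84, 0.76, 0.63
- SD 1.5, 50 per arm: 0.59 against 0.56, 0.51, 0.42
- SD 2.5, 50 per arm: 0.98 against 0.93, 0.85, 0.70

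Using t in place of normal quantiles widens each per-visit figure by only about 0.01.

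**The case against.** The strongest reply is that pain is already covered. SAP 4.4.1 promises tables and missing-value counts for every variable, and a two-sided comparison for continuous ones. That stands. A reader might infer that the plan has no analysis of pain at all, and the documents do not support that.

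A reader might also infer that silence in 4.4.5 causes the missing interval. It does not. Naming pain there would still give no interval, because 4.4.1 reserves intervals for primary and secondary outcomes. The gap needs both sections together.

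Third, no document requires an interval or baseline adjustment for a safety measure, and the SAP names no baseline-adjusted model for its continuous secondary outcomes either. Its change table makes adverse-event data descriptive only, so a light safety analysis is in keeping with the plan. This stands too: the point concerns specification and is neither a contradiction nor a source of bias. It is also tempting to say that protocol 8.1 already licenses a repeated-measures model for pain, but that list is tied to secondary outcomes.

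Fourth, the precision figures rest on assumptions, and the gain can be small. Per visit at SD 2 and 50 per arm it is 0.04, 0.10 or 0.22 points. Against change scores at correlation 0.7, which 4.4.1 would allow, it is about 0.05 (0.607 against 0.560). Exclusion (11) does not bound largest pain or later scores. All of this stands, and it is why the case rests mainly on the missing interval and only secondarily on precision.

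**Conclusion.** The point holds as a minor, optional improvement. Cancer pain is a declared safety assessment for which the plan promises tables and an unadjusted test, but no estimated difference, no interval and no use of baseline. The default comparison is unbiased, and neither the primary result nor the sample size is affected.

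That the plan promises no interval follows from the text alone. The size of the precision gain depends on the assumed SD and correlation, and the figures for the weeks 2-8 mean also on equal correlation across visits. At correlation 0.3 the per-visit gain is close to nothing; at 0.7 it is worthwhile.

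**What to change.** Add to SAP 4.4.5, worded as an exception so that it does not conflict with the default test in 4.4.1:

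> *As an exception to the default comparison in 4.4.1, mean and largest weekly NRS pain at weeks 2, 4, 6, 8 and 16 will each be analysed with a repeated-measures model containing treatment, visit, treatment-by-visit and baseline score, with unstructured covariance and all observed data. The EA-SA difference with 95% CI will be given at each visit and averaged over weeks 2-8. Mean intensity averaged over weeks 2-8 is the main summary. These are descriptive safety estimates, without significance tests.*

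Show beside them, by arm, the item (13) proportion whose opioid dose rose by at least 30%. Naming a main summary matters because two measures at five visits plus an average give 12 intervals. The per-visit estimates should stay, because an average can dilute a short-lived worsening.

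The cost is a few sentences and one table. Protocol section 3 already collects baseline and follow-up pain, and item (13) already requires opioid dose. The downside is a little more analysis work.
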